2.8.2 Deaths

If a meaningful number of cases of death is reported (i.e., 5 or more cases), deaths will be summarized. All deaths will be listed. Deaths occurring during the Extension Period will be flagged.

2.8.3 Laboratory data

For participants in Cohort 1 that do not have relevant laboratory test results in their medical history within 6 months prior to the Screening Visit, all laboratory data collected will be listed by participant and if normal ranges are available, abnormalities will be flagged.

2.8.4 Other safety data

2.8.4.1 MS Relapse

An MS relapse is defined as an appearance of a new neurological abnormality or worsening of previously stable or improving pre-existing neurological abnormality, separated by at least 30 days from onset of a preceding clinical demyelinating event (Polman et al 2011). The abnormality must have been present for at least 24 hours and occurred in the absence of fever (< 37.5°C) or a known infection.

If a meaningful number of cases of MS relapse is reported (i.e., 5 or more cases), MS relapse during the study will be summarized by cohort. All occurrence of MS relapse will be listed. Incidence of MS relapse during the Extension Period will be flagged.

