Participants in Cohort 2 will continue to administer of atumumab monthly until the final dose at Week 28. Novartis will supply of atumumab to participants in Cohort 2 for the Extension Period.

Cohort 2 participants may either remain on their commercially prescribed of atumumab or switch to study supplied of atumumab.

Participants in Cohort 3 will not enter the open-label Extension Period.

Study design schematics for Cohorts 1, 2 and 3 are shown in Figure 3-1, Figure 3-2 and Figure 3-3 respectively.

Figure 3-1 Study Design (Cohort 1)

[figure not shown]
[figure not shown]

Figure 3-2 Study Design (Cohort 2)

[figure not shown]

Figure 3-3 Study Design (Cohort 3)

4 Rationale

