2.1 Data analysis general information

The statistical analysis outlined in this SAP will be performed by Novartis or a designated Contract Research Organization (CRO), using SAS® version 9.4 or higher and stored in the Novartis Global Programming and Statistical Environment (GPS).

For continuous variables, summary statistics will include number of participants (n), mean, standard deviation, minimum, maximum, median and 25th and 75th percentiles (optional). For categorical variables, frequency counts and percentages will be reported.

Unless otherwise stated, all data summaries will be presented by cohort and on all participants in the respective analysis set.

The CSR analysis cut-off date will be the EOS1/EOS visit for participants who do not continue to the Extension Period, or the EOS2 visit for participants who continue into the Extension Period. All data collected prior to this date will be used for analysis.

All data (collected or derived) will be listed appropriately.

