2.8 Safety analyses

2.8.1 Adverse events (AEs)

An adverse event (AE) is any untoward medical occurrence (i.e., any unfavorable and unintended sign [including abnormal laboratory findings], symptom or disease) in a participant or clinical investigation of a participant after providing written informed consent for participation in the study. That means that a participant can report AEs before having started study medication. For reporting purposes, the main focus will be on any adverse event which started on or after the Week 0 visit.

The number (and percentage) of participants with AEs will be summarized by cohort in the following ways:

- by primary SOC and PT
- by primary SOC, PT and maximum severity
- by Standardized MedDRA Query (SMQ) and PT

Separate summaries will be provided for:

- serious adverse events (SAEs)
- AEs leading study discontinuation

Separate summaries will be presented for data collected during the Extension Period.

The MedDRA version used for reporting the study will be described in a footnote. If a particular Missing CTCAE grade will not be imputed. If a participant reported more than one AE with the same PT, the AE with the greatest severity will be presented. A participant with multiple AEs within a primary SOC is only counted once towards the total of the primary SOC.

All AEs will be listed by cohort.

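### Any by-cohort MS relapse summary would span the whole study, although Cohort 3 is followed to Week 4 and Cohorts 1 and 2 for up to 26 or 28 weeks

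*SAP*

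**What the plan says.** **Relapse.** SAP 2.8.4.1 makes the summary conditional: "If a meaningful number of cases of MS relapse is reported (i.e., 5 or more cases"). If that is met, "MS relapse during the study will be summarized by cohort". All relapses are listed whether or not it is met. The only provision for period is that "Incidence of MS relapse during the Extension Period will be flagged".

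**Data included.** SAP 2.1 sets the cut-off at EOS1/EOS for participants who do not continue, "or the EOS2 visit for participants who continue into the Extension Period. All data collected prior to this date will be used for analysis". The same section gives counts and percentages as the standard summary for categorical variables, by cohort unless stated otherwise.

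**Follow-up.** SAP 1.1 describes a 4-week Investigational Period starting at Week 0. The optional extension then takes Cohort 1 to Week 26 and Cohort 2 to Week 28. Protocol Section 3 states: "Participants in Cohort 3 will not enter the open-label Extension Period".

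**Adverse events.** SAP 2.8.1 says: "The number (and percentage) of participants with AEs will be summarized by cohort in the following ways". It gives a starting point, in that "the main focus will be on any adverse event which started on or after the Week 0 visit", and adds: "Separate summaries will be presented for data collected during the Extension Period". It does not say where the main tables end.

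**The concern.** The share of participants with at least one relapse grows with the time they are watched. A table that puts Cohort 3, seen for 4 weeks, beside cohorts that may be seen for 26 or 28 weeks mixes relapse rate with observation time. The direction is fixed by the design: the two ofatumumab cohorts would be expected to show more relapses than the iDMT cohort even if the drugs did not differ. The size of the gap also depends on how many participants choose the extension.

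A flag in a listing tells the reader which relapses came late. It does not change the numerator or the denominator of the by-cohort summary. In a descriptive study the tables are the product, and Cohort 3 is the reference group, so side-by-side relapse percentages invite comparison.

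**Working it through.** The documents give no relapse rate and no expected extension uptake, so there is no planned figure to reproduce. The calculation below is an illustration.

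**Inputs from the documents**
- 22 participants per cohort (SAP Section 3).
- Scheduled follow-up from Week 0: 4 weeks for everyone; 26 weeks (Cohort 1) or 28 weeks (Cohort 2) for those entering the extension; 4 weeks for all of Cohort 3 (SAP 1.1).

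**Assumptions**
- A constant relapse rate, the same in all cohorts: 0.2 per year, range 0.05 to 0.4.
- Extension uptake *u* of 50% or 100% in Cohorts 1 and 2.
- No drop-out. One year is 52.18 weeks.

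**Step 1: follow-up ratio.** 26/4 = 6.5 and 28/4 = 7.0. Counting the screening week as well, 27/5 = 5.4 and 29/5 = 5.8.

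**Step 2: person-weeks.** Cohort 1: 22 × (4 + 22*u*). Cohort 2: 22 × (4 + 24*u*). Cohort 3: 22 × 4.

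| Uptake | Cohort 1 | Cohort 2 | Cohort 3 | Total |
|---|---|---|---|---|
| 50% | 330 | 352 | 88 | 770 |
| 100% | 572 | 616 | 88 | 1,276 |

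The three Investigational Periods together supply 3 × 88 = 264 person-weeks. The extension therefore supplies 506/770 = 66% or 1,012/1,276 = 79% of the total, none of it from Cohort 3.

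**Step 3: expected percentage with at least one relapse.** P(w) = 1 − exp(−rate × w/52.18). At 0.2 per year, P(4) = 1.52%, P(26) = 9.49% and P(28) = 10.18%. Cohorts 1 and 2 are mixtures, *u*·P(26 or 28) + (1 − *u*)·P(4).

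| Rate per year | Uptake | Cohort 1 | Cohort 2 | Cohort 3 |
|---|---|---|---|---|
| 0.2 | 50% | 5.50% | 5.85% | 1.52% |
| 0.2 | 100% | 9.49% | 10.18% | 1.52% |
| 0.05 | 100% | 2.5% | 2.6% | 0.4% |
| 0.4 | 100% | 18.1% | 19.3% | 3.0% |

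At 0.2 per year the ratios to Cohort 3 are 3.62 and 3.84 with 50% uptake, and 6.23 and 6.69 with full uptake.

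**Step 4: how often the table would appear.** Expected relapses over the whole study at 0.2 per year are 0.2 × 770/52.18 = 2.95 (50% uptake) or 0.2 × 1,276/52.18 = 4.89 (full uptake). The Poisson chance of 5 or more is 18% or 54%.

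**Step 5: the common window.** Restricted to Week 4, every cohort has the same expected percentage, 1.52% at 0.2 per year, and the ratios are 1.0. Expected relapses in that window are 0.2 × 264/52.18 = 1.01 across all 66 participants, and the chance of 5 or more is about 0.4%. A trigger applied separately by period would therefore almost never produce the common-window table.

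**The case against.** The strongest reply is that little hangs on this table. It appears only with 5 or more cases, which at 0.2 per year is 18% to 54% likely. The full-uptake percentages correspond to about 2.1, 2.2 and 0.3 participants out of 22. Relapse is classed as other safety data and is not a listed endpoint, Cohort 3 is there as a reference for vaccine response, and no hypothesis is tested. SAP 2.4.1 also tabulates study duration by cohort in categories up to 24 weeks, so an attentive reader would see the imbalance. All of this stands and limits the consequence. None of it corrects the relapse summary itself. The trigger in fact works the other way: at such rates it would be met almost only because of extension follow-up.

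Three stronger readings are tempting, and the documents do not support them.

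- **That adverse events and serious adverse events are pooled over unequal follow-up.** SAP 2.8.1 gives extension data their own summaries, and the natural reading is that the main tables stop before the extension. The cut-off in SAP 2.1 defines the data available, not the window of each table. What remains is that the end of the main window is not stated.
- **That deaths are affected in the same way.** SAP 2.8.2 has the same 5-case condition and extension flag, but it names no by-cohort percentage.
- **That the sparser contact schedule in the extension adds to the distortion.** Fewer contacts would, if anything, lower detection in Cohorts 1 and 2, which is the opposite direction. Protocol 8.5 also requires participants to report symptoms at once.

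**Conclusion.** The point holds for MS relapse. Followed as written, SAP 2.8.4.1 yields a by-cohort summary in which maximum follow-up differs 6.5- to 7-fold, with nothing in the summary to adjust for it. Under equal true rates of 0.2 per year, the ofatumumab cohorts would be expected to show roughly 3.6 to 6.7 times the iDMT percentage, depending on uptake between 50% and 100%. The follow-up ratio comes from the documents. The percentages rest on assumed rates, assumed uptake, a constant hazard and no drop-out.

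For adverse events the finding is only a missing end date for the main tables. The primary seroprotection result is untouched. This is a modest, cheaply corrected flaw in a conditional safety table.

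**What to change.** In SAP 2.8.4.1, keep the 5-case trigger on the whole-study count. When it is met:

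- present relapses in the Investigational Period (to EOS1 for Cohorts 1 and 2, EOS for Cohort 3) for all three cohorts;
- present Extension Period relapses separately for Cohorts 1 and 2;
- accompany any whole-study figure with person-time and events per person-year.

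In SAP 2.8.1, add one sentence stating that the main by-cohort adverse event and serious adverse event tables end at EOS1/EOS.

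The cost is SAP wording and table shells. No new data are needed, because flagging extension relapses already requires each one to be assigned to a period. The drawback is that each table will hold few events.

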2.9 Pharmacokinetic endpoints

There are no pharmacokinetic endpoints planned for this study.

2.10 PD and PK/PD analyses

There are no PD and PK/PD analyses planned for this study.

2.11 Patient-reported outcomes

There are no patient-reported outcome analyses planned for this study.

2.12 Biomarkers

There are no biomarker analyses planned for this study.

2.13 Other analyses

No other analyses are planned for this study.

2.14 Interim analysis

For the purpose of earlier dissemination of results, an interim analysis will be performed after:

- all enrolled participants have completed the Investigational Period or discontinued the Investigational Period prematurely OR
- On/around March 29, 2021, whichever comes first.

Since there will be no hypothesis testing involved, statistical adjustment for the interim analysis will not be made at the stage of final analyses.

3 Sample size calculation

Sample size calculations were based on the proportion of participants who responded to influenza vaccination.

The sample size of 20 participants per arm is selected based on budget and need for early availability of results. The sample size of 20 subjects will provide estimates with margin of error (half-width of a 95% confidence interval) of 20.1%, 19%, and 17.5% corresponding to response rates of 70%, 75%, and 80%, respectively. Adjusting for 10% drop-out, 22 subjects will be enrolled in each arm.

4 Change to protocol specified analyses

There are no changes to protocol specified analyses.

5 Appendix

5.1 Imputation rules

5.1.1 Study drug

There will be no imputation rules for study drug detailed for this study.

5.1.2 AE date imputation

The following table explains the notation used in the logic matrix. Please note that missing start dates will not be imputed.

777	Day	Month	Year
Partial Adverse Event Start Date	Not used	MON	YYYY
Treatment Start Date (TRTSTD)	Not used	TRTM	TRTY

The following matrix explains the logic behind the imputation.

	MON MISSIN	MON <trtm< th="">MON=TRTM	MON>TRTM	</trtm<>	MON=TRTM	MON>TRTM
YYYY	NC	NC	NC	NC
MISSIN	Uncertain			
YYYY < TRTY	(D) Before Treatment Start	(C)	(C)	(C)
YYYY = TRTY	(B) Uncertain	(C) Before Treatment	(A) Uncertain	(A) After Treatment
YYYY > TRTY	(E) After Treatment Start	(A) After Treatment	(A) After Treatment	(A) After Treatment

The following table is the legend to the logic matrix.

If AE end date is complete and AE end date < Treatment start date or AE end date is partial and AE imputed end date < Treatment start date, then AE start reference = min (informed consent date, earliest visit date from SV) Else if AE end date is partial, AE end date > = Treatment start date or AE is ongoing, then AE start reference = treatment start date.

Relationship				
Before AE start reference	Partial date indicates AE start date prior to			
	AE start			
After AE start reference	Partial date indicates AE start date after AE			
	start			

Uncertain	Partial date insufficient to determine relationship of AE start date to AE start
Imputation Calculation	
NC/Blank	No convention
(A)	MAX(01MONYYYY, AE start reference+1
	day)
(B)	AE start reference+1

15MONYYYY

01JULYYYY

01JANYYYY
No date imputation

For business use only

Page 21 of 24

COMB157GUS12

Adverse Event End Date Imputation

Imputed date = date part of original date, if complete date

Imputed date = min (completion/discontinuation visit date, DEC 31, date of death), if month is missing

Imputed date = min (completion/discontinuation visit date, last day of the month, date of death), if day is missing

Imputed Date Flag

Complete date

Novartis

SAP

(C)

(D)

(E)

If year of the imputed date is not equal to YYYY then date flag = Y else if month of the imputed date is not equal to MON then date flag = M else if day of the imputed date is not equal to day of original date then date_flag = D else date flag = null.

5.1.3 Concomitant medication date imputation

This algorithm is used when *event* is the partial start date of the concomitant medication. The following table explains the notation used in the logic matrix. Please note that missing start dates will not be imputed.

	Day	Month	Year
Partial CM Start Date	Not used	MON	YYYY
Treatment Start Date (TRTSDT)	Not used	TRTM	TRTY

The following matrix explains the logic behind the imputation.

	MON	MON <trtm< th="">MON=TRTM	MON>TRTM	</trtm<>	MON=TRTM	MON>TRTM
	MISSING			
YYYY	(C2)	(C1)	(C1)	(C1)
MISSING	Uncertain	Uncertain	Uncertain	Uncertain
YYYY < TRTY	(D)	(A)	(A)	(A)
	Before	Before	Before	Before
	Treatment Start	Treatment Start	Treatment Start	Treatment Start

YYYY = TRTY	(C2) Uncertain	(A) Before Treatment Start	(C1) Uncertain	(B) After Treatment Start
YYYY > TRTY		(B) After Treatment Start	(B) After Treatment Start	(B) After Treatment Start

The following table is the legend to the logic matrix.

Relationship		
Before Treatment Start	ore Treatment Start Partial date indicates CMD start date prior to Treatment Start Date	
After Treatment Start	Partial date indicates CMD start date after Treatment Start Date	
Uncertain Partial date insufficient to determine relationship of		
	date relative to Treatment Start Date	
Imputation Calculation		
(A)	15MONYYYY	
(B)	01MONYYYY	
(C1 or C2)	IF relative reference start = before treatment start THEN	
	TRTSDT-1	
f.	ELSE IF relative reference start = ' ' THEN TRTSDT+1	
(D)	01JULYYYY	
(E)	01JANYYYY	

Concomitant Medication End Date Imputation

If not ongoing then

Imputed date = date part of CMENDTC, if complete date

Imputed date = min(completion/discontinuation visit date, DEC 31), if month is missing. (C2, D, E)

Imputed date = min(completion/discontinuation visit date, last day of the Month), if day is missing. (A, B, C1)

Concomitant Medication Date Flag

If not a complete date then

Y - If year of the imputed date is not equal to YYYY else M - If month of the imputed date is not equal to MON else D.

5.1.3.1 Prior therapies date imputation

Same as above.

5.1.3.2 Post therapies date imputation

Same as above.

5.1.3.3 Other imputations

Non-responder imputation

Non-responder imputation (NRI) assumes that a participant is a treatment failure if they discontinue the study prematurely. Hence, for missing data the primary variable outcome of achieving seroprotection as defined by a post vaccination HI titer ≥40 (Yes/No) at Week 4 will be imputed to "No".

5.2 AEs coding/grading

Adverse events will be coded using the Medical Dictionary for Regulatory Activities (MedDRA) The latest MedDRA version will be used and will be described in the footnote of relevant outputs.

5.3 Laboratory parameters derivations

Not applicable.

5.4 Statistical models

Primary analysis

There is no hypothesis testing planned for this study.

Key secondary analysis

There is no key secondary analysis planned for this study.

Rule of exclusion criteria of analysis sets

Deviation ID	Description of deviation	Exclusion in analyses
INCL01A	No informed consent obtained or missing.	Exclude from the SAF.
INCL05	Not Planning to receive a 2020-2021 inactivated influenza vaccine	Exclude from the SAF
INCL06A	Not Planning to start treatment with ofatumumab for Cohort 1	Exclude from the SAF
INCL06B	Not already on commercially prescribed ofatumumab for Cohort 2 with minimum 4 weeks	Exclude from the SAF
INCL07	Currently not be receiving iDMT for Cohort 3	Exclude from the SAF

Analysis set	PD ID that cause participants to be excluded	Non-PD criteria that cause participants to be excluded
SAF	INCL01A	Influenza vaccine not taken
SAF	INCL05	Influenza vaccine not taken

Analysis set	PD ID that cause participants to be excluded	Non-PD criteria that cause participants to be excluded
SAF	INCL06A	Study treatment not taken
SAF	INCL06B	Study treatment not taken
SAF	INCL07	Study treatment not taken

6 Reference

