- **Population:** Relapsing MS participants subdivided into three cohorts. (1) Receiving inactive influenza vaccine two weeks prior to starting of atumumab 20 mg subcutaneous treatment; (2) Receiving inactive influenza vaccine after at least 4 weeks of commercial ofatumumab 20 mg subcutaneous treatment (3) receiving inactive influenza vaccine while on injectable disease modifying therapy (iDMT).
- **Variable:** Achieving seroprotection as defined by a postvaccination antibody titer ≥ 40 (yes/no) at Week 4
- Treatment of interest: Inactivated influenza vaccination either two weeks prior to of a tumumab start or at least 4 weeks after of a tumumab start or while on iDMT.
- **Intercurrent event:** None
- **Summary measure:** Proportion of subjects achieving seroprotection

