6.1.2 Treatment cohorts/group

- Cohort 1: RMS participants receiving a 2020-2021, 2021-2022, or 2022-2023 inactivated influenza vaccine at least two week prior to ofatumumab start.
- Cohort 2: RMS participants receiving a 2020-2021, 2021-2022, or 2022-2023 inactivated influenza vaccine at least 4 weeks after of atumumab start.
- Cohort 3: RMS participants currently on a prescribed iDMT receiving a 2020-2021, 2021-2022, or 2022-2023 inactivated influenza vaccine.

6.1.3 **Post-Trial Access**

Participants in Cohort 1 and 2 that successfully complete the Investigational Period may either continue into the optional, 6-month open-label Extension Period or will be referred to the commercial participant services hub for post-trial continuity of treatment, where the benefit/risk is acceptable and discussed with the participant, investigator and if applicable, the participant's treating physician. Participants who do not complete the study or withdraw due to an of atumumab related AE or SAE should follow-up with their treating physician for continued treatment options.

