DMS Document Management System EMA European Medicines Agency

EOS End of Study
FAS Full Analysis Set

GPS Global Statistical and Programming Environment

HI Hemagluttination Inhibition

IA Interim Analyses
MS Multiple Sclerosis

MedDRA Medical Dictionary for Drug Regulatory Affairs

NRI Non-responder Imputation

PK Pharmacokinetics

PRO Patient-reported Outcomes

PT Preferred Term

QIV Quadrivalent inactivated influenza vaccine

RAP Reporting & Analysis Process
RMS Relapsing Multiple Sclerosis
SAE Serious Adverse Event
SAF Safety Analysis Set
SAP Statistical Analysis Plan
SAS Statistical Analysis System

sc Subcutaneous

SOC System Organ Class

TEAE Treatment Emergent Adverse Events

TFLs Tables, Figures, Listings

iDMT Injectable Disease Modifying Therapy

1 Introduction

The purpose of this Statistical Analysis Plan (SAP) is to describe the statistical methods planned in Section 12 of the Clinical Study Protocol (CSP) version 00 (release date 10 November 2020) for the clinical trial COMB157GUS12 and any additional analyses, specifications or deviations from this planned protocol before clinical database lock (CDBL).

This SAP will be used to draft the Clinical Study Report (CSR) Section 9.7: Statistical methods and IA plans.

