2.2 Analysis sets

Safety set

The Safety Set (SAF) comprises all participants who have received the 2020-2021 inactivated influenza vaccine.

Unless stated otherwise, the SAF will be used for all summary tables and listings.

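### SAP 2.2 and SAP 5.4 define different Safety Sets: a vaccinated participant with deviation INCL06A, INCL06B or INCL07 is in under one and out under the other

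*SAP*

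**What the plan says.** **Membership by vaccination.** SAP 2.2 says that the SAF "comprises all participants who have received the 2020-2021 inactivated influenza vaccine". It adds: "Unless stated otherwise, the SAF will be used for all summary tables and listings". No other set is defined; the abbreviation list has "FAS Full Analysis Set", but the SAP never uses it. SAP 2.5 (primary analysis) and 2.8 (safety) name no set, so the SAF applies to both.

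**Membership by deviation.** Two tables at the end of SAP 5.4 list reasons for leaving the SAF.

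- The first attaches "Exclude from the SAF" to five codes. Three of them concern background therapy: INCL06A (Cohort 1, no plan to start ofatumumab), INCL06B ("Not already on commercially prescribed ofatumumab for Cohort 2 with minimum 4 weeks") and INCL07 (Cohort 3, no current iDMT).
- The second puts a further criterion beside each code. For INCL01A (no consent) and INCL05 (not planning vaccination) it is that the vaccine was not taken. For INCL06A, INCL06B and INCL07 it is "Study treatment not taken".

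**Cohort 2 entry.** Protocol 2.1 describes the cohort as "Receiving inactive influenza vaccine after at least 4 weeks of commercial ofatumumab 20 mg subcutaneous treatment"; Protocol 6.1.2 and SAP 1.1 agree. Inclusion criterion 6 (Protocol 5.1) asks for only 2 weeks on ofatumumab before screening, and Protocol 3 places vaccination within 9 calendar days after screening.

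**Missing titers.** Protocol 12.4.4 and SAP 2.5.3 count a missing post-vaccination titer as non-response (NRI).

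**The concern.** Two parts of one SAP give different rules for who is in its only analysis set. Section 2.2 does not point to 5.4, and 5.4 does not say that it modifies 2.2. Analysts following one or the other would report different denominators for the primary rate and different AE tables.

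The safety consequence is the plainer one. SAP 2.1.1 makes the vaccine the treatment of interest, yet 5.4 would take vaccinated people out of the AE summaries because of their background therapy.

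For the seroprotection rate, the direction depends on who is removed. A Cohort 2 participant with a short lead-in would normally have a Week 4 titer, so removal can move the rate either way. A Cohort 1 participant who was vaccinated, never started ofatumumab and has no usable titer is a failure under NRI; removal deletes that failure and can only raise the rate.

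**Working it through.** **1. The two rules side by side**

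| Participant | SAP 2.2 | SAP 5.4 |
|---|---|---|
| Vaccinated, no deviation | In | In |
| Vaccinated, with INCL06A, INCL06B or INCL07 | In | Out |
| Vaccinated, Cohort 1, never starts ofatumumab | In | Out, if the study-treatment criterion means ofatumumab or iDMT and excludes on its own |
| Not vaccinated | Out | Out through the vaccine criterion |

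The second row needs no interpretation. The third does: 5.4 words the vaccine criterion and the study-treatment criterion differently, which suggests that the latter means ofatumumab or iDMT, but the SAP does not define the term.

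**2. Can someone who met criterion 6 be INCL06B?**

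Days on ofatumumab at vaccination = days at screening + 0 to 9.

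- 14 days at screening: 14 + 0 = 14 to 14 + 9 = 23, below 28.
- 18 days at screening: at most 18 + 9 = 27, below 28. So 14 to 18 days never reaches 4 weeks.
- 19 days at screening: 19 + 9 = 28. So 19 to 27 days depends on the vaccination day.
- 28 days or more at screening always reaches it.

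This counts the 4 weeks at vaccination. Counted at screening, everyone with 14 to 27 days falls short.

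**3. The plan's own precision**

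Protocol 12.8.1 and SAP 3 give half-widths of 20.1%, 19% and 17.5% for 20 per arm at rates of 70%, 75% and 80%. The formula 1.96 × √(p(1−p)/20) gives 20.08, 18.98 and 17.53 points, so these reproduce. The planned exact (Clopper-Pearson) intervals have half-widths of 21.2, 20.2 and 19.0 points at 14/20, 15/20 and 16/20.

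**4. Effect on the rate**

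The documents do not say how many participants would be affected. The plan enrols 22 per arm to allow for 10% drop-out from 20, so 1 or 2 of 22 is assumed.

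*Two Cohort 1 never-starters without a usable titer, at the planned rates:*

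| Responders | SAP 2.2 with NRI (exact 95% CI) | Removed under SAP 5.4 (exact 95% CI) | Gap (points) |
|---|---|---|---|
| 14 | 14/22 = 63.6% (40.7–82.8) | 14/20 = 70.0% (45.7–88.1) | 6.4 |
| 15 | 15/22 = 68.2% (45.1–86.1) | 15/20 = 75.0% (50.9–91.3) | 6.8 |
| 16 | 16/22 = 72.7% (49.8–89.3) | 16/20 = 80.0% (56.3–94.3) | 7.3 |

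With one such participant the rates become 14/21 = 66.7%, 15/21 = 71.4% and 16/21 = 76.2%, gaps of 3.0, 3.2 and 3.5 points.

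*Cohort 2 entry deviators with titers, starting from 15/22 = 68.2%:*

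- Remove one non-responder: 15/21 = 71.4% (47.8–88.7). Remove one responder: 14/21 = 66.7% (43.0–85.4).
- Remove two, of whom 0, 1 or 2 are responders: 15/20 = 75.0%, 14/20 = 70.0% or 13/20 = 65.0%.

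**The case against.** **Reconciling the rules.** The default clause in 2.2 might be read as yielding to 5.4. But it governs which set an output uses, not who belongs to the set. The second table in 5.4 could mean the deviation together with treatment not taken, which would remove fewer people. The first table's instruction is nevertheless unconditional, so the conflict remains.

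**Criterion 6.** A reader might infer that every eligible Cohort 2 participant with a short lead-in will be removed. The documents do not support that. INCL06B does not say when the 4 weeks are counted, or whether someone who satisfied criterion 6 would be given that code. The SAP implements protocol version 00, whereas the available criterion 6 is from version 03. The amendment summaries mention no change to the 2-week figure but may be incomplete. The 2-week and 4-week texts also already differ within the protocol; SAP 5.4 did not create that difference.

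**Never-starters.** It is tempting to say that they are always NRI failures because an early EOS1 visit precedes the Day 25 to 35 Week 4 window in SAP Table 2-1. That is not firm. SAP 2.4.1.1 applies the tabulated windows to measurements taken at every visit and provides others for less frequent assessments, and the post-vaccination titer is scheduled only at Week 4. Protocol 9.1.1 also asks people who stop treatment to return for EOS1. Some never-starters may therefore have a usable titer.

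**A third definition.** Protocol 12.1 bases its Safety Set on study drug, which might look like another competing rule. The term is ambiguous: the protocol glossary defines study treatment broadly, and Protocol 6.1.1 lists the vaccine under study treatments. The wording supports no more than that.

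**Partial cover elsewhere.** SAP 2.3.1 tabulates deviations, SAP 2.1 lists all data and SAP 2.8.1 lists all AEs. The cases should be visible in listings; the AE summaries and the rate remain exposed.

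**Estimand.** Protocol 2.1 defines the population by cohort timing, so leaving never-starters and short lead-ins out of the primary rate is defensible. This stands: the SAF should hold everyone vaccinated, but the denominator of the rate is partly a choice.

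**Conclusion.** The conflict between SAP 2.2 and 5.4 is certain on the text and should be fixed. Under 5.4 as written, vaccinated participants with INCL06A, INCL06B or INCL07 leave the AE summaries and the primary denominator.

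Two extensions are conditional. INCL06B reaches people who met criterion 6 only if the 4 weeks are counted at or before vaccination and version 00 carried the same 2-week figure. Cohort 1 never-starters are removed only if the undefined study-treatment criterion means ofatumumab or iDMT, and the upward shift holds only for those without a usable titer.

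The size is modest: about 3 points for one non-responder, with 6.4 to 7.3 points an upper bound that takes both planned drop-outs as never-starters without titers. All of these are below the planned half-widths, and SAP 5.4 plans no hypothesis test. A reader might infer from 68.2% becoming 71.4% that the conflict decides whether a cohort meets the 70% seroprotection criterion in SAP 2.7. That goes too far: the counts are assumed, and meeting any one of the three criteria there is enough. The harm is an undefined denominator and incomplete AE summaries.

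SAP 2.2 names only the 2020-2021 vaccine, so vaccinated here means vaccinated in that season.

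**What to change.** 1. In SAP 5.4, keep only missing informed consent and influenza vaccine not taken as SAF exclusions. Remove the exclusions for INCL06A, INCL06B and INCL07 and the study-treatment criterion beside them. INCL05 then matters only where the vaccine was not given.
2. Word SAP 2.2 to match, so that the SAF is all consented, vaccinated participants, and state that all AE summaries use it.
3. In SAP 2.2, name one denominator for the primary NRI rate: either the SAF, with the rate excluding entry deviators and never-starters as supplementary, or a separately defined immunogenicity set matching the cohort definitions, with the SAF rate as supplementary. Report the number removed by cohort in either case.
4. Reconcile inclusion criterion 6, the Cohort 2 definition and INCL06B, and state when the lead-in is counted. No minimum is proposed here.

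**Cost.** Items 1 to 3 need SAP wording and one extra table, with no new data. Any change to the protocol text under item 4 needs a written amendment (Protocol 14.1). The downside is that a few participants outside the cohort definitions stay in the safety tables.
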